This trial will be conducted in compliance with the protocol, current version of the World Medical Association Declaration of Helsinki, the recent International Council on Harmonisation – Good Clinical Practice guidelines and all applicable national and local regulations.

TRIAL SCHEDULE

Figure 1: Trial Design

aGVHD=acute graft versus host disease; CR=complete response (of lower GI-aGVHD); D=Day; GI=gastrointestinal; iSRC=Independent Safety Review Committee; R=randomization

1. Review of the first six subjects randomized to two treatment arms
2. Exact dose depends on the weight of a subject a baseline (randomization/Day 0)
3. Apraglutide will be administered weekly for 8 weeks (Week 0 to Week 7, inclusive). Treatment can be continued up to 13 weeks (Week 8 to Week 12, inclusive) if a CR is not achieved at Week 8. If there is no CR at Week 13 optional treatment is allowed for a maximum of 13 weeks (Week 13 to Week 25, inclusive) or until a complete lower GI-aGVHD response is achieved, whichever comes first. Optional treatment can only be started if additional apraglutide treatment would benefit the subject based on the Investigator's assessment. Treatment can be re-started in case of a lower GI-aGVHD flare during follow-up (between Week 9 and Week 25) at the same dose given at randomization/Day 0 providing that apraglutide treatment was previously stopped if a lower GI-aGVHD CR was achieved at Day 56 (or a PR or CR was achieved at Day 91). Only one re-treatment course is allowed and should not last more than 13 weeks

Table 1: Schedule of Assessments - Screening, Baseline, Treatment, and Optional Treatment

Assessments	Screening ¹	Baseline /First dose	Treatment visits Week 1 – Week 7 ²							Treatment visits Week 8 – Week 12 – In case of no CR at Week 8 ³				Optional Treatment visits ⁴ If no CR at Week 13			
			Lower GI-aGVHD flare treatment after CR is achieved ⁵							Lower GI-aGVHD flare treatment after CR is achieved ⁶							
Visit No. /RT/eCRF use	1	2	3	4	5	6	Dosing	7	Dosing	8	Dosing	9	Dosing	10	Dosing	11	Dosing
Week	0	1	2	3	4	5	6	7	8	9, ¹⁰ 11,12	13	14, ¹⁵ 16	17	18, ¹⁹ 20	21	22, 23, 24, 25	
Day	0	7	14	21	28	35	42	49	56	91	119			147			
Visit Window ⁶	-84 to -1 days	0	±1 day	±1 day	±1 day	±1 day	±1 day	±1 day	±1 day	±1 day	±1 day	±1 day	±1 day	±1 day	±1 day	±1 day	±1 day
General																	
Informed consent	X																
Inclusion and exclusion criteria	X	X															
RUX start ⁷	X	X															
Randomization ⁸	X																
Demographics																	
Medical, surgical and disease history	X																
Prior and concomitant medication	X	X	X	X	X	X	X	X	X	X	X	X	X	X	X	X	X
Hospitalization status	X	X	X	X	X	X	X	X	X	X	X	X	X	X	X	X	X
Safety																	
Colonoscopy/CT colonography ⁹																	
MR enterography ⁹	X																
Lower GI biopsy ¹⁰	X																
Physical examination	X	X	X	X	X	X	X	X	X	X	X	X	X	X	X	X	X
Twelve-lead ECG ¹¹	X	X	X	X	X	X	X	X	X	X	X	X	X	X	X	X	X
Vital signs ¹²	X	X	X	X	X	X	X	X	X	X	X	X	X	X	X	X	X
Body weight and height ¹³	X	X	X	X	X	X	X	X	X	X	X	X	X	X	X	X	X
Adverse events	X	X	X	X	X	X	X	X	X	X	X	X	X	X	X	X	X
Pregnancy test ¹⁴	X	X	X	X	X	X	X	X	X	X	X	X	X	X	X	X	X
Local labs ¹⁵	X	X ¹⁶	X	X	X	X	X	X	X	Bilirubin only	X	Bilirubin only	X	Bilirubin only	X	Bilirubin only	X
Viral load ¹⁷		X															
Central Lab																	
Albumin, citrulline, calprotectin, microbiome		X ¹⁸	X	X	X	X	X	X	X	X	X	X	X	X	X	X	X
Blood biomarkers		X ¹⁸	X	X	X	X	X	X	X	X	X	X	X	X	X	X	X

TMP no.: TMP-CD-04_1
 Version no.: 1.0
 TMP effective date: 10-Oct-2019

Proof-of-concept trial of apaglutide in GVHD

Assessments	Screening ¹ Baseline /First dose	Treatment visits Week 1 – Week 7 ²							Treatment visits Week 8 – Week 12 In case of no CR at Week 8 ³				Optional Treatment visits ⁴ If no CR at Week 13					
		Visit No. /RT/eCRF use	1	2	3	4	5	6	Dosing	7	Dosing	8	Dosing	9	Dosing	10	Dosing	11
Week		0	1	2	3	4	5	6	7	8	9, 10, 11, 12	13	14, 15, 16	17	18, 19, 20	21	22, 23, 24, 25	
Day		0	7	14	21	28	35	42	49	56	91	119		119		147		
Visit Window⁶	-84 to -1 days	0	±1 day	±1 day	±1 day	±1 day	±1 day	±1 day	±1 day	±1 day	±1 day							
Blood samples for pre-dose PK ¹⁹	X	X	X	X	X	X	X	X	X	X	X	X	X	X	X	X	X	X
Blood samples for post-dose PK (6, 30, 72, 120, and 168 h) ²⁰	X																	
Blood samples for ADA ²¹	X ¹⁸	X	X	X	X	X	X	X	X	X	X	X	X	X	X	X	X	X
Stool sample collection ²²	X	X	X	X	X	X	X	X	X	X	X	X	X	X	X	X	X	X
Other assessments																		
Survival and disease progression		X	X	X	X	X	X	X	X	X	X	X	X	X	X	X	X	X
Parenteral support ²³	X	X	X	X	X	X	X	X	X	X	X	X	X	X	X	X	X	X
MAGIC assessment ²⁴	X	X	X	X	X	X	X	X	X	X	X	X	X	X	X	X	X	X
Questionnaires ²⁵	X	X	X	X	X	X	X	X	X	X	X	X	X	X	X	X	X	X
Trial medication																		
Subcutaneous injection of IMP ²⁶	X	X	X	X	X	X	X	X	X	X	X	X	X	X	X	X	X	X

ADA=anti-drug antibody; aGVHD=acute graft versus host disease; CR=complete response; CT=computed tomography; ECG=electrocardiogram; IMP=investigational medicinal product; MAGIC= Mount Sinai Acute Graft Versus Host Disease International Consortium; MR=magnetic resonance; PK=pharmacokinetics; RUX=ruxolitinib; VectivBio=VectivBio, Inc.

Proof-of-concept trial of aprotinin in GVHD

Footnotes to Table 1:

1. The screening process can start any time after clinical diagnosis of lower GI-aGVHD and SS initiation; obtaining informed consent should be done before any other trial procedure:
 - If needed, screening can be performed on the same day as baseline, as long as all assessments required at screening and baseline are performed and the results are available **prior to randomization**
 - If the same assessment is foreseen at screening and baseline, and screening and randomization occur on the same day, then the assessment does not need to be repeated
 - 2. Treatment should be continued until Week 7 inclusive, even if a complete lower GI-aGVHD response is achieved before Week 7 inclusive
 - 3. If a lower GI-aGVHD CR is not achieved at Week 8, treatment should be continued until Week 12 inclusive; even if a CR is achieved before Week 12
 - 4. Optional treatment can start, if there is no complete lower GI-aGVHD response at Week 13 and if the Investigator considers that the subject could benefit from the **additional aprotinin treatment**. Treatment can continue for a maximum 13 weeks (until Week 25, inclusive) or until a complete lower GI-aGVHD response is achieved, whichever comes first
 - 5. In case of lower GI-aGVHD flare, treatment can be re-started at the same dose given at randomization/Day 0 (e.g., if flare occurs at Week 17, treatment will be performed during visits at Weeks 17–25 or until a CR is achieved, whichever comes first). Treatment can continue for a maximum of 13 weeks (until Week 25, inclusive) or until a complete lower GI-aGVHD response is achieved, whichever comes first
 - 6. All visit procedures are recommended to be done on the same day, unless specified otherwise
 - 7. Ruxolitinib treatment should be initiated concomitantly with aprotinin (in exceptional cases where concomitant administration is not possible, RUX should be administered at maximum 72 hours before aprotinin initiation)

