	
>2 mg/kg/day methylprednisolone [MP] equivalent), whichever occurs first, with at least 182 days of follow-up
 
Duration of response from Day 28 (median and range) on the total MAGIC score where duration of response is defined as the interval from the Day 28 response (PR and CR) to death or new systemic therapy for aGVHD (including an increase in steroids
 
>2 mg/kg/day MP equivalent), whichever occurs first, with at least 182 days of follow-up
 
Individual duration of lower GI response (according to the MAGIC score) counted from the first response to return to baseline or worse
 
Individual duration of lower GI response (according to the MAGIC score) in subjects that were re-treated with apaglutide because of a lower GI-aGVHD flare, counted from the first response after apaglutide restart to return to baseline or worse
 
Time to partial lower GI-aGVHD response (median and range) as defined by the MAGIC score
 
Time to complete lower GI-aGVHD response (median and range) as defined by the MAGIC score
 
Best overall response defined as overall response (PR or CR) at any time point up to and including Day 91 and before the start of additional systemic therapy for lower GI-aGVHD
 
Failure-free survival up to 2 years post-first dose of apaglutide
 
Non-relapse mortality up to 2 years post-first dose of apaglutide
 
Incidence of malignancy relapse up to 2 years post-first dose of apaglutide
 
Overall survival up to 2 years post-first dose of apaglutide
 
Incidence of graft failure up to 2 years post-first dose of apaglutide
 
Incidence of lower GI-aGVHD flare up to Day 182 after the first apaglutide dose following earlier cessation due to complete lower GI-aGVHD response
 
Cumulative SS and RUX doses from start of the RUX treatment up to Day 91 after the first dose of apaglutide

--	--

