	
methods comparing the observed results in each treatment arm with a historical control dataset.
 
Analysis
 
An interim analysis will be performed when 17 subjects have either reached Day 56 or withdrawn from the trial. All available data points by the data cut-off date will be included in the analysis.
 
The final analysis will be done in two steps. The primary analysis of safety and efficacy will be performed once all subjects have either completed Day 91 or withdrawn from the trial. Additional analyses will be done once all the subjects have either completed the EOT visit or withdrawn from the trial. A Clinical Trial Report (CTR) will be issued after the primary analysis. An addendum to the CTR will cover the follow-up period until 2 years after the first apaglutide dose.
 
Sample Size
 
Up to 34 subjects with SR lower GI-aGVHD who are taking BAT will be randomized in this trial. The sample size justification was based on a selected secondary endpoint (Day 56 GI response). Observed response rates of 5/7 (71%) subjects at the interim analyses will lead to a high probability (>88%) of effectiveness comparing apaglutide and BAT with a historical Day 56 response rate derived from the previous trial, REACH2, including a 10% penalty.
 
Analysis Sets
 
The Full Analysis Set (FAS) comprises all enrolled subjects (randomized and non-randomized LBWs). All efficacy evaluations will be conducted using the FAS according to the planned dose (high dose, low dose, LBW dose) and in total.
 
The LBW Analysis Set comprises all subjects with a body weight ranging from 40.0 to <50.0 kg assigned to receive 2.5 mg apaglutide who actually received at least one dose of therapy and who have provided at least one post-baseline assessment for any endpoint. All endpoints will be analyzed for this set separately.
 
Safety Analysis Set 1 (SAS1) comprises all randomized subjects exposed to either of the two randomized apaglutide dose levels. All principal safety analyses will be carried out on the SAS1 according to the dose of apaglutide received.
 
Safety Analysis Set 2 (SAS2) comprises all randomized and non-randomized subjects exposed to any apaglutide

--	---

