## 1 INTRODUCTION

This Statistical Analysis Plan (SAP) for Final Analysis (FA) describes the procedures and timeline for the Final Analysis specified in the protocol TA799-101 5.0, FINAL, 27/MAR/2023 ([VectivBio AG 2023](#)). For the rationale and aim of the trial, please refer to the *protocol* for details. The Final analysis will be done in two steps. The Primary analysis of safety and efficacy will be performed once all subjects have either completed Day 91 or withdrawn from the trial. Additional analyses will be done once all the subjects have either completed the end of trial (EOT) visit or withdrawn from the trial. This additional analysis will be referred to as “EOT analysis”.

The Primary Analysis targets the characterization of the safety profile and the obtention of efficacy results. It will be used to support the Clinical Trial Report (CTR). The EOT analysis will feed an addendum to the CTR that will cover the follow-up period until 2 years after the first apaglutide dose.

All decisions regarding Primary analysis, as defined in the present SAP document, have been made prior to database snapshot for the Primary analysis. This SAP FA consists of an extension of the SAP of the Interim Analysis (IA) performed for this trial.

The clinical cut-off date for the Primary analysis will be when all enrolled subjects have either reached Day 91 or withdrawn from trial: up to 01 Dec 2023 (included). All available data points by the clinical cut-off date will be included in the Primary analysis; at the time of the data extract, all data points after the clinical cut-off date will be programmatically cut. Data extracted from the electronic data capture (EDC) system and data transferred from external vendor sources (e.g., lab data) will be mapped into the Study Data Tabulation Model (SDTM, v1.7 and implementation guidelines SDTMIG 3.3) datasets which will be used as the source data for the Primary analysis. Note that the technical procedures and steps for processing these data and for implementing the definitions of variables for the purpose of the statistical analysis are covered in the analysis datasets specifications document (programming cut-off, analysis data model, ADaM, v2.1 and implementation guidelines ADaMIG 1.2).

The Final Analysis will be performed under single-blind design of the trial. Actual treatments will be mapped into the SDTM. Details of the unblinding procedure are described in the Trial Blinding Plan.

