Unless specified otherwise, endpoints described in this document will be analyzed at both analysis steps: Primary Analysis and EOT Analysis.

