### 3.2 Secondary endpoints:

- Overall response rate at Day 56 on the lower GI tract MAGIC stage: defined as proportion of subjects with complete response (CR) or partial response (PR) on the lower GI tract MAGIC stage at Day 56.
- Overall response rate (PR and CR) at Days 14, 28, 91, 119, 147, and 182 on the lower GI tract MAGIC stage.
- Overall response rate (PR and CR) at Days 14, 28, 56, 91, 119, 147, and 182 by organ system (skin, lower and upper GI tract, and liver) on the total MAGIC grade.
- Proportion of all subjects who achieve a CR or PR at Day 28 and maintain a CR or PR at Day 56 [Only for Primary Analysis].
- Individual duration of lower GI response (according to the MAGIC score)
  - counted from the first response to return to baseline or worse
  - in subjects that were re-treated with apaglutide because of a lower GI-aGVHD flare, counted from the first response after apaglutide restart to return to baseline or worse
- Time to:
  - Partial lower GI-aGVHD response as defined by the MAGIC score
  - Complete lower GI-aGVHD response as defined by the MAGIC score
- Duration of response from Day 56 on the total MAGIC score: defined as the interval from the Day 56 response (PR and CR) to death or new systemic therapy for aGVHD (including an increase in steroids >2 mg/kg/day methylprednisolone (MP) equivalent), whichever occurs first, with at least 182 days of follow-up
- Duration of response from Day 28 on the total MAGIC: defined as the interval from the Day 28 response (PR and CR) to death or new systemic therapy for aGVHD (including an increase in steroids >2 mg/kg/day MP equivalent), whichever occurs first, with at least 182 days of follow-up
- Best overall response defined as overall response (PR or CR) at any time point up to and including Day 91 and before the start of additional systemic therapy for lower GI-aGVHD [Only for Primary Analysis]
- Failure-free survival up to 2 years post-first dose of apaglutide
- Incidence of malignancy relapse up to 2 years post-first dose of apaglutide [Only for EOT Analysis]
- Non-relapse mortality up to 2 years post-first dose of apaglutide

- Overall survival up to 2 years post-first dose of apaglutide [Only for EOT Analysis]
- Incidence of lower GI-aGVHD flare up to Day 182 after the first apaglutide dose following earlier cessation due to complete lower GI-aGVHD response
- Incidence of graft failure up to 2 years post-first dose of apaglutide [Only for EOT Analysis]

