#### *4.3.9.11 Incidence of malignancy relapse up to 2 years post-first dose of apaglutide*

The malignancy relapse/progression time is defined as the time from the date of the first dose to the date of hematologic malignancy relapse/progression.

Hematologic malignancy relapse/progression will be identified by manual review of reported malignancies or relapses in the AE data against the Underlying disease history CRF by the medical team, and confirmed with Sponsor. The list of identified hematologic malignancy relapse/progression will be finalized prior to the data base lock both for the Primary and the EOT analysis.

The malignancy/relapse progression will be summarized using Kaplan-Meier estimator. The number and percentage of subjects experiencing an event, and subjects censored will be summarized by apaglutide dose levels and in total. The median time-to-event will be presented where possible, along with the range and the associated two-sided 95% Brookmeyer-Crowley confidence interval. The event-free rate with 95% CI using Greenwood's formula will be provided for selected time points (e.g., 1, 3, 6, 12 and 24 months).

Plots of the Kaplan-Meier estimate for the malignancy/relapse progression will be presented by apaglutide dose levels and in total.

Subject for which no malignancy/relapse progression event occurs will be right censored at their last follow-up visit.

Incidence of malignancy/relapse progression will be analyzed only for the EOT analysis.

*4.3.9.12 Overall Survival up to 2 years post-first dose of apaglutide*

The overall survival time is defined as the time from the date of the first dose to the date of death due to any cause.

The last date known to be alive for each individual subject may be determined using, but not limited to, the following dates recorded on the eCRF:

- AE start and stop dates
- Study treatment start and stop dates
- Sample collection date for laboratory assessments
- Dates of any performed visit
- Start and stop dates of concomitant medications

Subjects who are alive at the time of data cut-off will be right censored on the date the subject was last known to be alive.

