The overall survival time will be summarized using Kaplan-Meier estimator. The number and percentage of subjects experiencing an event (death), and subjects censored will be summarized by apaglutide dose levels and in total. The median time-to-event will be presented where possible, along with the range and the associated two-sided 95% Brookmeyer-Crowley confidence interval.

Plots of the Kaplan-Meier estimate for the overall survival will be presented by apaglutide dose levels and in total.

Overall Survival will be analyzed only for the EOT analysis.

*4.3.9.13 Non-relapse Mortality up to 2 years post-first dose of apaglutide*

The non-relapse mortality time is defined as the time from the date of the first dose to the date of death not preceded by hematologic malignancy relapse/progression.

The non-relapse mortality will be summarized using Kaplan-Meier estimator. The number and percentage of subjects experiencing an event, and subjects censored will be summarized by apaglutide dose levels and in total. The median time-to-event will be presented where possible, along with the range and the associated two-sided 95% Brookmeyer-Crowley confidence interval. The event-free rate with 95% CI using Greenwood's formula will be provided for selected time points (e.g., 1, 3, 6, 12 and 24 months).

Plots of the Kaplan-Meier estimate for the non-relapse mortality will be presented by apraglutide dose levels and in total.

Subject for which “hematologic malignancy relapse/progression” event occurs will be right censored at the time of occurrence of the event.

Subject for which neither “death” or “hematologic malignancy relapse/progression” event occurs will be right censored at their last follow-up visit.

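### Overall survival and malignancy relapse are held to the end-of-trial analysis while non-relapse mortality and failure-free survival are reported at the Primary Analysis, so the main report has no mortality estimate that counts deaths after relapse

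*Protocol*

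**What the plan says.** The protocol (Synopsis, and Sections 2.2 and 7.1) plans the final analysis in two steps. For the first it says: "The primary analysis of safety and efficacy will be performed once all subjects have either completed Day 91 or withdrawn from the trial". The second follows the EOT visit and feeds an addendum covering follow-up to two years. Among the secondary endpoints the protocol lists "Overall survival up to 2 years post-first dose of apaglutide", and it lists malignancy relapse, NRM and FFS over the same horizon. It does not assign any of these four to one step only.

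The SAP (Section 1) fixes the primary cut-off at the point when all enrolled subjects have "reached Day 91 or withdrawn from trial: up to 01 Dec 2023 (included"). It then sets a default: "Unless specified otherwise, endpoints described in this document will be analyzed at both analysis steps: Primary Analysis and EOT Analysis".

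In SAP 3.2, "Non-relapse mortality up to 2 years post-first dose of apaglutide" carries no restriction, and neither does FFS, so both fall under the default. Overall survival is tagged: "Overall survival up to 2 years post-first dose of apaglutide [Only for EOT Analysis"]. Malignancy relapse has the same tag. The method sections repeat this. SAP 4.3.9.11 says: "Incidence of malignancy/relapse progression will be analyzed only for the EOT analysis". SAP 4.3.9.12 says: "Overall Survival will be analyzed only for the EOT analysis".

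**The concern.** NRM is one part of a set. In this population death without relapse and relapse are competing outcomes, and all-cause survival shows what they add up to. Reporting NRM without the other two leaves the reader unable to tell whether a given NRM figure goes with few or many relapses, or what total mortality was in each dose group.

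This matters more than usual here because safety is the primary objective, and Protocol 1.8.1 names possible acceleration of neoplastic growth as a risk of the drug class. Immaturity does not explain the split, since NRM and FFS are just as immature at the primary cut-off. Missing inputs do not explain it either. SAP 4.3.9.11 says the list of relapses is finalised before both database locks, and NRM cannot be computed without death dates and relapse status.

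**Working it through.** The plan gives no figure for this delay or its effect, so there is none to reproduce.

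**1. Which endpoint is reported when**

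| Endpoint (SAP section) | Horizon | Primary Analysis | EOT | Role of relapse |
|---|---|---|---|---|
| NRM (4.3.9.13) | 2 years | yes | yes | censors the subject |
| FFS (4.3.9.14) | 2 years | yes | yes | is an event, ends follow-up |
| Malignancy relapse (4.3.9.11) | 2 years | no | yes | is the event |
| Overall survival (4.3.9.12) | 2 years | no | yes | ignored, all deaths count |

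**2. Following one subject who relapses and then dies before the cut-off**

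- NRM: censored at relapse, so the death is not an event.
- FFS: the event is the relapse, or earlier additional systemic therapy. The death adds nothing.
- Duration of response (4.3.9.7, 4.3.9.9): death is an event, but only among responders and pooled with loss of response or new therapy. It is not a mortality estimate.
- Adverse events (4.3.8.1): a fatal event appears in a Grade 5 table, either treatment-emergent (to 28 days after the last dose) or post-treatment. These tables give counts by term and overall, by dose, without time to event.

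So no mortality or survival estimate at the Primary Analysis counts this death.

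**3. Length of the wait**

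Inputs: Day 91, Day 728 (Week 104, window ±4 weeks) and the cut-off of 01 Dec 2023.

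- 728 − 91 = 637 days; 637 / 30.44 = 20.9 months.
- With visit windows (±1 day and ±28 days): 608 to 666 days, or 20.0 to 21.9 months.
- If the last subject reached Day 91 on the cut-off date: 01 Dec 2023 + 637 days = 29 Aug 2025 (01 Aug to 26 Sep 2025 with the ±4 weeks).
- Protocol Section 12 allows up to 12 months for each report. The gap between the main report and the addendum could therefore be 20.9 − 12 ≈ 9 months to 20.9 + 12 ≈ 33 months.

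**4. How many deaths could be involved (assumed rates, not in the documents)**

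Assume constant hazards, 12-month NRM p₁ = 30%, 12-month relapse p₂ = 10% to 30%, median survival after relapse m = 2 to 3 months, and N = 34.

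- λ = −ln(1 − p₁ − p₂)/12; λ₂ = λ·p₂/(p₁ + p₂); λ₃ = ln 2/m.
- Relapse by t: R(t) = (λ₂/λ)(1 − e^(−λt)).
- Death after relapse by t: R(t) − λ₂(e^(−λt) − e^(−λ₃t))/(λ₃ − λ).

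For p₂ = 20%, m = 3 and t = 3: λ = 0.0578, λ₂ = 0.0231, λ₃ = 0.231. This gives relapse 0.064 (2.2 subjects) and death after relapse 0.018 (0.6 subjects).

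| Follow-up | Relapses of 34 | Deaths after relapse of 34 |
|---|---|---|
| 3 months | 1.0 to 3.5 | 0.3 to 1.4 |
| 6 months | 1.9 to 6.2 | 0.9 to 3.8 |

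As a share of 34 subjects, 0.3 to 3.8 deaths is about 1 to 11 percentage points.

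**5. Crude NRM against all-cause mortality (assumed counts)**

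Take 30 subjects, 5 non-relapse deaths and 3 deaths after relapse. Crude NRM is 5/30 = 16.7%; all-cause mortality is 8/30 = 26.7%. The 10-point difference is what an overall survival analysis would show. The three deaths are purely illustrative.

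**6. Direction of any effect on NRM**

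With the same counts and no other censoring, 1 − KM for NRM is 5/30 = 16.7% if the relapses come after the deaths, and 1 − 22/27 = 5/27 = 18.5% if they come before. Censoring at relapse does not push the Kaplan-Meier figure below the crude one.

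**The case against.** The strongest answer is that most of the information is in the main report already. Relapses are FFS events and are identified from adverse-event data, so they also appear in those tables. Grade 5 events are counted by dose with an overall row in two non-overlapping periods. SAP 4.3.8.3 tabulates a treatment-emergent category covering the whole neoplasms class, including events leading to death. This stands. A reader might infer that relapses and later deaths are absent from the main report, and the documents do not support that. What is missing is a relapse incidence, an all-cause survival estimate, and a mortality estimate that includes deaths after relapse.

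A reader might also infer that relapse makes NRM look better. That fits only the crude percentage. The planned estimator is Kaplan-Meier, and step 6 shows that censoring at relapse does not lower it below the crude figure.

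Third, the SAP may fairly allocate endpoints to steps. The protocol is silent on the allocation and gives the two-year follow-up to the addendum, and the sentence on Day 91 sets only a trigger. Section 6 also omits the other timing tags, such as graft failure at EOT only. So this is not a direct contradiction of the protocol. It remains an unexplained departure from the SAP's own default, which separates endpoints that need to be read together.

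Finally, safety oversight does not wait for either report: the independent committee reviews data during the trial. That protects subjects, but it does not supply the missing summaries. Nothing in the documents suggests a data-driven choice; the SAP states that decisions on the Primary Analysis preceded the database snapshot.

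**Conclusion.** The point holds as a gap in what is summarised and when. At the Primary Analysis NRM and FFS are shown without overall survival or relapse incidence, although all four share the two-year horizon and the inputs exist at that lock. The two missing analyses come about 21 months later (20.0 to 21.9 with visit windows). This assumes that the last subject reached Day 91 at the cut-off and completes Week 104; it would be shorter if the last subject reached Day 91 earlier or left the trial early.

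The number of deaths affected is unknown. On the assumed rates it is about 0.3 to 3.8 of 34 at three to six months, so the effect could be negligible or could approach 11 percentage points of mortality. The gap changes no estimand and no decision rule in this descriptive trial. It is worth correcting because the main safety report would otherwise lack all-cause mortality over time by dose, and correction is cheap.

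**What to change.** In SAP 3.2, delete the EOT-only tag for overall survival and for malignancy relapse. Delete the matching closing sentences in 4.3.9.11 and 4.3.9.12. Produce both at the Primary Analysis with the same cut-off as NRM and FFS, and repeat them at EOT.

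Do not bring the relapse analysis forward as Kaplan-Meier alone. SAP 4.3.9.11 censors subjects without relapse, including those who die, and 4.3.9.13 gives only Kaplan-Meier for NRM. Protocol 7.8.2 also calls for cumulative incidence where risks compete. Add cumulative incidence for relapse, with death without relapse as the competing event, and for NRM, with relapse as the competing event. State in the SAP that these outputs treat the other event as competing and do not censor it.

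If the sponsor keeps the deferral, it should be listed in Section 6 with its reason. That documents the choice but leaves the gap.

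The cost is a table and figure for each of the two endpoints, plus the cumulative-incidence outputs. They use the relapse list already finalised for the primary lock, the death dates needed for NRM, and last-known-alive dates from the case report form. The downside is early estimates with wide intervals, as for NRM and FFS.
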